Ocular Adverse Events

Ocular AEs are frequently reported with tisotumab vedotin. Events of conjunctivitis have been mainly CTCAE Grade 1 and 2. In May 2016, an initial ocular mitigation plan (OMP) was implemented upon reporting of the first case of Grade 3 conjunctivitis with irreversible damage in a patient given 0.9 mg/kg 3Q4W in the GEN702 trial. This plan was further updated in September 2016 after 2 patients in the GEN701 trial experienced Grade 2 conjunctivitis with conjunctival scarring. Due to an event of Grade 4 keratitis in the GEN701

dose expansion cohort (Part II), an urgent safety measure and a more comprehensive OMP were implemented across both GEN701 and GEN702 trials in December 2016. Elements of this ocular mitigation plan included the addition of ocular premedications for all patients (cooling eye pads during tisotumab vedotin infusion, vasoconstrictor eye drops immediately prior to treatment with study drug, prophylactic treatment with topical ophthalmic steroid eye drops, use of lubricating eye drops throughout study treatment) and dose modifications for ocular events.

Ocular AEs with Q3W tisotumab vedotin

As of 16 Aug 2019, 396 patients have received tisotumab vedotin on a Q3W schedule. The most frequent ocular AEs were conjunctivitis (29.5%), dry eye (20.7%), lacrimation increased (6.1%), vision blurred (6.1%), blepharitis (5.1%), and keratitis (4.8%).

Since implementation of the December 2016 comprehensive OMP, both the frequency and severity of conjunctivitis, the most frequently reported ocular AE in relation to treatment with tisotumab vedotin, have been reduced. The frequency of conjunctivitis decreased from 44.2% to 25.9% in subjects dosed Q3W and only one subject has experienced a Grade 3 event after Dec-2016 (no Grade 4 or 5 events have been observed either before or after Dec-2016). [Table 1](#) and [Figure 1](#) summarize the decreased frequency and severity of conjunctivitis.

Table 1: Frequency of conjunctivitis* by CTCAE toxicity grading before and after Dec-2016 – subjects dosed Q3W

[figure not shown]
Maximum Grade	Before** (N=104)	After*** (N=274)	Total (N=378)
	N (%)	N (%)	N (%)
Any conjunctivitis event	46 (44.2)	71 (25.9)	117 (31.0)
Grade 1	17 (16.3)	30 (10.9)	47 (12.4)
Grade 2	25 (24.0)	40 (14.6)	65 (17.2)
Grade 3	4 (3.8)	1 (0.4)	5 (1.3)
Grade 4	0 (0.0)	0 (0.0)	0 (0.0)
Grade 5	0 (0.0)	0 (0.0)	0 (0.0)

* Including the preferred term ‘conjunctivitis’

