** Including subjects that received first dose of tisotumab vedotin 1Q3W before 22-Dec-2016 OMP

*** Including subjects that received first dose of tisotumab vedotin 1Q3W after 22-Dec-2016 OMP

Figure 1: Frequency of the conjunctivitis* by CTCAE toxicity grading before and after Dec-2016 – subjects dosed Q3W

* Including the preferred term ‘conjunctivitis’

All but one Grade 3 event of keratitis (including subjects dosed before and after Dec-2016) were non-serious events \leq Grade 2. Events of ulcerative keratitis observed in subjects dosed Q3W have decreased in severity after implementation of the Dec-2016 OMP; one serious Grade 4 event was reported prior to Dec-2016 whereas no serious events of ulcerative keratitis have been reported in subjects dosed after Dec-2016 (all non-serious events were \leq Grade 2 with the exception of one event that was Grade 3).

Ocular AEs with Dose Dense Regimens

A total of 29 patients received 0.9 mg/kg or 1.2 mg/kg tisotumab vedotin on a dose-dense schedule in the GEN702 trial. None of the 3 patients treated with 3Q4W 0.9 mg/kg tisotumab vedotin were subject to the comprehensive ocular mitigation plan in the GEN702 study as all were treated prior to December 2016. One of the patients treated at 0.9 mg/kg 3Q4W experienced an event of Grade 3 conjunctivitis and Grade 2 symblepharon.

A total of 26 patients received 1.2 mg/kg 3Q4W tisotumab vedotin in the GEN702 trial. The 6 patients treated during dose escalation were treated prior to Dec 2016. The comprehensive OMP was inconsistently applied to the remaining 20 patients in the expansion cohort.

Prophylactic steroid eye drops were not administered on subsequent dosing days after the first week for most patients. In addition, many patients with ongoing ocular events continued to receive tisotumab vedotin in GEN702 as they were treated prior to GEN702 Amendment 4, when dose adjustments due to ocular events became more restrictive. Grade 3 or higher ocular events were seen in 6 patients (23%) treated with 1.2 mg/kg tisotumab vedotin, including 5 patients (19%) with Grade 3 or higher symblepharon.

Since December 2016, the comprehensive ocular mitigation plan has been modified with additional measures for toxicity management (see Section 5.3.1).

For further details regarding clinical safety data with tisotumab vedotin, please refer to the Investigator Brochure.

Adverse Events of Special Interest

Three Adverse Events of Special Interest (AESI) have been identified:

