5.2.3 Dose Modifications

For patients who do not tolerate the protocol-specified dosing schedule, dose reductions are permitted in order to allow the patient to continue tisotumab vedotin treatment. Dose reductions must be preapproved by the sponsor's medical monitor unless allowed according to the mitigation plans specified in the protocol (please refer to Section 5.3). Once a dose is reduced, it should not be re-escalated for that patient during the study.

- If toxicities occur on Day 1 of any cycle and require the tisotumab vedotin dose to be held, then the start of the cycle may be delayed.
- If toxicities occur on Day 8 and require the dose to be held for >2 days, then the dose should be eliminated.
- If toxicities occur on Day 15 of any cycle and require the dose to be held >7 days, then the dose(s) should be eliminated.
- If a patient only receives tisotumab vedotin on Day 1 and needs to skip Days 8 and 15, the patient could resume the next cycle as early as Day 22 (new Day 1) per the mitigation plans specified in Section 5.3.

In case any dose reduction of tisotumab vedotin is needed, the dose must be reduced according to the guidelines provided below (Table 3 and Table 4)

Table 3: Dose modification scheme: Dose-dense regimen

Previous dose of tisotumab vedotin	Reduced dose of tisotumab vedotin
1.2 mg/kg (120 mg maximum total dose) on D1, D8, and D15	0.9 mg/kg (90 mg maximum total dose) on D1, D8, and D15
0.9 mg/kg (90 mg maximum total dose) on D1, D8, and D15	0.65 mg/kg (65 mg maximum total dose) on D1, D8, and D15
0.65 mg/kg (65 mg maximum total dose) on D1, D8, and D15	0.65* mg/kg (65 mg maximum total dose) on D1 and D8

* If the patient is already being treated with tisotumab vedotin 0.65 mg/kg on D1 and D8, the dose must not be reduced further.

Table 4: Dose modification scheme: Q3W regimen

Previous dose of tisotumab vedotin	Reduced dose of tisotumab vedotin
2.0 mg/kg (200 mg maximum total dose)	1.3 mg/kg (130 mg maximum total dose)
1.3 mg/kg (130 mg maximum total dose)	0.9* mg/kg (90 mg maximum total dose)

* If the patient is already being treated with tisotumab vedotin 0.9 mg/kg, the dose must not be reduced further.

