Conjunctivitis Grade 2 2nd occurrence	Hold dose of tisotumab vedotin: 
• If the event has improved to baseline within 6 weeks (calculated from the onset date of the 2nd Grade 2 event), reduce next dose of tisotumab vedotin according to Section 5.2.3.	Prophylaxis with topical antibiotic drops should be also be considered. Additional treatment modalities such as topical lubricating drops, topical immunomodulator drops (such as calcineurin inhibitors or equivalent), treatment with systemic steroids or surgical intervention to be determined as clinically applicable by the local ophthalmologist.
Conjunctivitis Grade 2 3rd occurrence	If the event does not improve to baseline within 6 weeks, permanently discontinue tisotumab vedotin.	Treatment to continue until the local ophthalmologist deems necessary.
Conjunctivitis \geq Grade 3	Permanently discontinue tisotumab vedotin.	
Keratitis		
Keratitis Grade 1	Hold dosing until event is managed effectively. Continue same dose for next dosing	Local ophthalmologist must prescribe frequent dosing of topical steroid drops.
Keratitis Grade 2 1st occurrence	Hold tisotumab vedotin until event has improved to \leq Grade 1. Reduce tisotumab vedotin according to Section 5.2.3.	Local ophthalmologist must prescribe frequent dosing of topical steroid drops (prednisolone 1% or equivalent, overnight treatment with a topical steroid ophthalmic ointment, such as loteprednol etabonate, can be considered). Prophylaxis with topical antibiotic drops should be also be considered. Additional treatment modalities such as topical lubricating drops, topical immunomodulator drops (such as calcineurin inhibitors or equivalent), treatment with systemic steroids or surgical intervention to be determined as clinically applicable by the local ophthalmologist.
Keratitis \leq Grade 2 2nd occurrence	Hold tisotumab vedotin until event has improved to \leq Grade 1. Reduce tisotumab vedotin again according to Section 5.2.3.	Treatment to continue until the local ophthalmologist deems necessary.
Keratitis \leq Grade 2 3rd occurrence	Permanently discontinue tisotumab vedotin.	
Keratitis \geq Grade 3	Permanently discontinue tisotumab vedotin.	

		Guidelines for Treatment Prescribed by the Ophthalmologist	
AE and Toxicity Grade (CTCAE v5.0)	Action Taken with Tisotumab Vedotin		
Conjunctival ulceration and ophthalmological findings of fluorescent patches must be handled as below			

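### Table 5 gives two incompatible dosing instructions for a Grade 1 keratitis event that follows a Grade 2 keratitis event

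*Protocol*

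**What the plan says.** The keratitis block of Protocol Table 5 (Section 5.3.1) has five rows.

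- **Grade 1**, no occurrence number: "Hold dosing until event is managed effectively. Continue same dose for next dosing".
- **First occurrence**, labelled "Keratitis Grade 2 1st occurrence", that is, exactly Grade 2: hold until Grade 1 or better, then reduce one level.
- **Second occurrence**, labelled ≤Grade 2: hold until Grade 1 or better, then "Reduce tisotumab vedotin again according to Section 5.2.3".
- **Third occurrence**, labelled ≤Grade 2: permanent discontinuation.
- **Grade 3 or higher**: permanent discontinuation.

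Section 5.3.1 bases the action on the CTCAE v5.0 grade. Section 5.2.3 sets the dose steps (Tables 3 and 4) and makes reductions one-way: "Once a dose is reduced, it should not be re-escalated for that patient during the study". It requires medical-monitor approval before a reduction, "unless allowed according to the mitigation plans specified in the protocol".

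**The concern.** A Grade 1 event after an earlier Grade 2 event is a Grade 1 keratitis, so the first row applies. It is also a repeat of Grade 2 or lower, so a repeat row applies. One row keeps the dose; the other lowers it again or ends treatment. Two sites could treat the same recurrence differently and both be compliant.

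The consequences cannot be reversed: a reduction is permanent and a stop is final. One reading may end treatment for a mild event. The other may keep dosing unchanged in a patient with repeated corneal toxicity. Ocular events are adverse events of special interest, and keratitis has a history in this programme. Section 1.3.3.1 introduces the December 2016 urgent safety measure with "Due to an event of Grade 4 keratitis in the GEN701" expansion cohort.

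**Working it through.** **Step 1: match events to rows.** The plan states no figure to reproduce here; the check is one of logic.

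| Keratitis sequence | Grade 1 row | Repeat rows (≤Grade 2) | Conflict |
|---|---|---|---|
| Grade 2, then Grade 2 | does not apply | reduce again | no |
| Grade 2, then Grade 1 | same dose | reduce again | yes |
| Grade 2, then a repeat, then Grade 1 | same dose | stop permanently | yes |

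Grade 1 followed by Grade 1 is left out of the concern. The first-occurrence row is for Grade 2, and the word *again* in the second-occurrence row presupposes an earlier reduction.

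**Step 2: look for a tie-break.** Sections 5.2.3, 5.3 and 5.3.1 contain no precedence rule and no definition of an occurrence. CTCAE grade does not decide it, because Grade 1 selects both rows.

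**Step 3: compare the other blocks of Table 5.** Conjunctivitis and the other-ocular-toxicities block label repeats as exactly Grade 2. Conjunctival ulceration uses Grade 1–2 for every occurrence below Grade 3 and has no separate Grade 1 row. Only keratitis has the overlap.

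**Step 4: size the difference at the second event.** Inputs are the dose steps in Tables 3 and 4. Weekly dose is mg/kg × doses per cycle ÷ weeks per cycle. In every case the first Grade 2 event has already cost one reduction.

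| Starting regimen | Start (mg/kg/week) | Same dose (Grade 1 row) | Reduced again (repeat row) |
|---|---|---|---|
| Q3W 2.0 mg/kg | 2.0/3 = 0.667 | 1.3/3 = 0.433 (35% below start) | 0.9/3 = 0.300 (55% below) |
| Dose-dense 0.9 | 0.9×3/4 = 0.675 | 0.65×3/4 = 0.488 (28% below) | 0.65×2/4 = 0.325 (52% below) |
| Dose-dense 1.2 | 1.2×3/4 = 0.900 | 0.9×3/4 = 0.675 (25% below) | 0.65×3/4 = 0.488 (46% below) |
| Dose-dense 0.65 | 0.65×3/4 = 0.488 | 0.65×2/4 = 0.325 (33% below) | 0.325, no lower step |

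The further step is therefore a cut of 31% (1 − 0.9/1.3) on Q3W, 33% (1 − 0.325/0.4875) from a 0.9 start, and 28% (1 − 0.65/0.9) from a 1.2 start. For the 0.65 start the readings agree at this event, because of the Table 3 footnote: "If the patient is already being treated with tisotumab vedotin 0.65 mg/kg on D1 and D8, the dose must not be reduced further". At the third event they differ in every regimen: continue or stop.

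**Step 5: size the affected group.** Section 1.3.3.1 reports any-grade keratitis in 4.8% of 396 Q3W patients. Applied to this trial, that is 0.048 × 30 = 1.4 patients in a Q3W arm, or 0.048 × 100 = 4.8 if that arm is expanded. These are ceilings: the group at issue needs a Grade 2 event and then a Grade 1 recurrence. The section also says "All but one Grade 3 event of keratitis (including subjects dosed before and after Dec-2016) were non-serious events" of Grade 2 or lower, so these rows cover nearly all keratitis seen on Q3W. It gives no split between Grades 1 and 2, no recurrence rate, and no keratitis rate for the dose-dense schedule.

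**The case against.** The strongest reply is that ordinary reading settles it: a row written for a numbered occurrence overrides a general row. The protocol does not say so, and its own wording is mixed. The ≤ sign in both repeat rows favours the stricter rule. But a Grade 1 event already meets the second-occurrence hold condition, and the conjunctivitis and other-ocular repeat rows say exactly Grade 2; both favour the looser one. Choosing between them is a clinical decision for the sponsor, and that part of the objection stands.

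Read literally, the third-occurrence row, which lacks the word *again*, could also catch three Grade 1 events. That is a further reason to define an occurrence.

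The table's extraction from PDF is visibly damaged in places, so a label error cannot be excluded from the text alone. The ≤ sign appears in both repeat rows, which makes an isolated misread unlikely.

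The numbers are small and the events mild. Grade 3 and above has its own clear row. The Grade 4 event predates the December 2016 plan, and Section 1.3.3.1 appears to list it under ulcerative keratitis, with no serious ulcerative keratitis in Q3W patients first dosed afterwards. All of this stands and limits the weight of the point.

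There are safeguards: reporting of every ocular event within 24 hours (Section 7.7.8.4), ophthalmology referral sought within 3 days (Section 5.3.1), real-time sponsor review and an SMC that includes the investigators with enrolled patients (Section 7.7), and site training (Section 8.1). They make lasting divergence less likely, but none says which row applies. Pre-approval does not help either: Table 5 is itself a mitigation plan, so a reduction it allows is exempt.

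**Conclusion.** The concern holds. Table 5 is wrong as written for a Grade 1 keratitis that follows a Grade 2 keratitis: two rows apply and their actions cannot both be followed. The second-event difference is a further cut of 28% to 33% in weekly dose (none for a 0.65 mg/kg start). The third-event difference is continuation against permanent discontinuation in every regimen.

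This rests on the ≤ labels being as printed and on counting occurrences from the first Grade 2 event. The number of patients affected is small and cannot be estimated from the documents. The point concerns dosing safety and consistency between sites; it does not touch the endpoint, sample size, analysis sets or interim rule. It should be corrected at the next amendment.

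**What to change.** Relabel the Grade 1 row *Keratitis Grade 1, no prior Grade 2 keratitis*, and keep ≤Grade 2 on the two repeat rows. Add three sentences: *Occurrences are counted from the first Grade 2 keratitis event. Any new Grade 1 or Grade 2 event after it counts as the next occurrence. For a Grade 1 repeat, hold dosing until the event is managed effectively.* The last sentence is needed because the existing hold condition has no force for a Grade 1 event.

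The stricter rule is the default because it is the only one under which the ≤ sign on the repeat rows has any meaning. If the sponsor confirms that the looser rule was intended, the repeat rows should instead read Grade 2, and every Grade 1 event should follow the Grade 1 row. Send sites a clarification letter in either case.

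The cost is one row label, three sentences and a letter, with no change to visits, sample size or analysis. The downside of the stricter rule is that a few patients with mild recurrence will have a further reduction or stop treatment.

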5.3.2 Infusion-Related Reactions

Tisotumab vedotin may cause IRRs including severe hypersensitivity or anaphylaxis. Signs and symptoms usually develop during or shortly after drug infusion.

- In case any clinical significant IRR is observed during or after the first infusion of tisotumab vedotin or at subsequent treatment cycles, the patient should be observed for 2 hours after the end of tisotumab vedotin administration for all subsequent infusions.
- At all times during infusion, immediate emergency treatment of an anaphylactic reaction according to institutional standards must be assured. In order to treat possible anaphylactic reactions, for instance, dexamethasone 10 mg and epinephrine in a 1:1000 dilution or equivalents must always be available along with equipment for assisted ventilation.
- All premedication must be reported on the concomitant medication page in the eCRF.

Dose modification and toxicity management guidelines for tisotumab vedotin associated infusion reaction are provided in [Table 6](#).

Table 6: Dose modification and toxicity management for infusion-related reactions

Infusion-Related Reactions (IRRs)	
Grade 1	Continue infusion at the investigator's discretion at half the infusion rate under close medical supervision.
Grade 2	Infusion must be interrupted and appropriate medical management instituted. The infusion may be re-started at the investigator's discretion at half the infusion rate under close medical supervision, if symptoms have resolved to \leq Grade 1 within an hour. The patient should be pre-medicated (antihistamine, acetaminophen and corticosteroids are recommended) before the next infusion.
Grade 3 1st occurrence	Infusion must be interrupted and appropriate medical management instituted. The infusion may be re-started at the investigator's discretion at half the infusion rate under close medical supervision if symptoms have resolved to \leq Grade 1 within an hour. The patient should be pre-medicated (antihistamine, acetaminophen and corticosteroids are recommended) before the next infusion.
Grade 3 2nd occurrence despite premedication	Permanently discontinue tisotumab vedotin treatment.
\geq Grade 4	Infusion must be interrupted immediately and appropriate medical therapy must be administered. Permanently discontinue tisotumab vedotin treatment.

5.3.3 Other Adverse Events

AEs such as increased bleeding, hemorrhage, elevated liver enzymes, mucositis, neutropenia, and peripheral neuropathy may be associated with tisotumab vedotin administration. Dose modification and toxicity management are provided in [Table 7](#).

Table 7: Dose modification and toxicity management for other AEs associated with tisotumab vedotin

Bleeding Events	

 Control vital signs and ensure stabilization of the patient according to local standards. Prompt evaluation to identify the underlying etiology of the bleeding event. Management should ultimately be dictated by the underlying diagnosis. Control laboratory coagulation and hematologic parameters including PT, aPTT, fibrinogen, platelets, INR and hemoglobin as soon as possible. 	
All Patients	
Any grade pulmonary or CNS hemorrhage	Permanently discontinue tisotumab vedotin treatment.
Patients NOT on anticoagulation therapy	
1st occurrence	Hold dosing until:
Hemorrhage (other) ¹ Grade 3	
 a) Bleeding has resolved. b) Blood hemoglobin level is stable. c) There is no bleeding diathesis that could increase the risk of continuing therapy. d) Patients must not have tumors involving or adjacent to major blood vessels 
When the above criteria are fulfilled the patient can resume treatment with tisotumab vedotin at the same dose as prior to the event.

≥2nd occurrence	Contact sponsor in order to discuss whether the patient may continue or must permanently discontinue tisotumab vedotin treatment.
Hemorrhage (other) ¹ Grade 3	
Hemorrhage Grade 4 (any occurrence)	Patient must permanently discontinue tisotumab vedotin treatment
Patients on anticoagulation therapy	
INR >2.5	
Patients on therapeutic anticoagulation whose INR is >2.5 prior to infusion of tisotumab vedotin must hold tisotumab vedotin until INR is ≤2.5. Patients may resume tisotumab vedotin administration immediately after the INR is ≤2.5.
 
Strongly consider holding anticoagulation until the above parameters are met.

Hemorrhage (other) ^a Grade 3	
Hold anticoagulation therapy.
 
Contact sponsor in order to discuss whether the patient may continue or must permanently discontinue tisotumab vedotin treatment.

Hemorrhage Grade 4 (any occurrence)	Patient must permanently discontinue tisotumab vedotin treatment
Liver parameters elevated (AST, ALT, or bilirubin)	
≥Grade 3	Hold tisotumab vedotin until toxicity resolves to ≤Grade 1. In the event of recurrence of ≥Grade 3, permanently discontinue tisotumab vedotin.
Mucositis	
Grade 3	Hold tisotumab vedotin until event has improved to ≤Grade 2, then reduce tisotumab vedotin according to Section 5.2.3. Treat according to local practice. In the event of recurrence to Grade 3, permanently discontinue tisotumab vedotin.
Grade 4	Permanently discontinue tisotumab vedotin.

Neutropenia	
Grade 3 or 1st occurrence of Grade 4	Hold tisotumab vedotin until event has improved to \leq Grade 2 (including G-CSF administration). Growth factor support (G-CSF) should be given prophylactically prior to subsequent tisotumab vedotin administrations.
2nd occurrence Grade 4	Contact sponsor to discuss dose reduction or discontinuation of tisotumab vedotin.
Peripheral neuropathy (including preferred terms as: neuropathy peripheral; peripheral sensory neuropathy; peripheral motor neuropathy; polyneuropathy)	
Grade 2 and 3	Hold tisotumab vedotin until event has improved to \leq Grade 1.
Initial or worsening of pre-existing condition	Reduce next dose according to dose reduction scheme in Section 5.2.3.
\geq Grade 4	Permanently discontinue tisotumab vedotin.

a Any other hemorrhage with the exception of pulmonary or CNS hemorrhage.

5.3.4 Storage and Handling

Refrigeration should be set at 2–8°C for storage of vials and solutions containing tisotumab vedotin. The controlled location must be accessible only to the pharmacist, the investigator, or a duly designated person. Tisotumab vedotin does not contain preservatives; therefore, opened and reconstituted vials should be used within 24 hours of preparation. If not used immediately, the in-use storage should not be longer than 24 hours. It is recommended that tisotumab vedotin vials and solutions be stored protected from direct sunlight until the time of use. Reconstituted vials must not be shaken.

Drug accountability procedures are provided in the Pharmacy Binder.

